Vaccine / Treatment Visit:	SCREENING		Day 1	Day 15 (+/- 3 days)	Day 22 (7 +/- 3 days after day 15)	Day 29 (14 +/- 3 days after day 15)	Day 43 (14 +/- 3 days after day 29)	Day 57 (14 +/- 3 days after day 43)	Day 64 (7 +/- 3 days after day 57)	Day 71 (14 +/- 3 days after day 57)	Day 85 (14 +/- 3 days after day 71) – 3 month	Day 106 (21 +/- 3 days after day 85)	Day 127 (21 +/- 3 days after day 106)	Day 148 (21 +/- 3 days after day 127)	Day 169 (21 +/- 3 days after day 148) – 6 m	9-month F/U (84 +/- 10 days after day 169)	OFF STUDY 12-month F/U – (84 +/- 10 days after 9month
	Within 6 weeks of day 1	Within 4 weeks of day 1															
History and Physical Exam																	
History	X																
Consent	X																
Physical Exam, ECOG PS		X	X		X		X		X		X	X	X	X	X	X	X
Tox assessment ^a		X	X	X	X	X	X	X	X	X	X	X	X	X	X	X	X
Lab Tests																	
CBC	X		X		X		X		X		X ^g	X	X	X	X	X	X
Chemistry panel ^f	X		X		X		X		X		X ^g	X	X	X	X	X	X
PT/INR		X ^k									X ^k						
Serum testosterone	X																
PSA and PAP	X		X		X		X		X		X ^g	X	X	X	X	X	X
Procedures																	
CT chest/abdomen/pelvis	X										X ^{gj}				X ^{hj}	X ^{hj}	X ^{ij}
Bone scan ^l	X										X ^g				X ^h	X ^h	X ⁱ
Leukapheresis		X ^b													X ^{bh}		
FLT PET scan ^m		X ^c									X ^g						
Tissue biopsy ^m		X ^d									X ^g						
Tetanus immunization		X ^e															
Blood for immune analyses		X					X				X				X	X	X
Blood for CTC analysis		X					X				X				X	X	X
Treatments																	
DNA immunization			X	X		X	X	X		X							
Pembrolizumab infusion			X		X		X		X								

^a Study coordinator or research nurse review of systems

^b For patients unable to undergo leukapheresis, a 200-mL blood draw (green top tubes) may be performed instead

^c FLT PET scan – within 4 weeks (28 days) of day 1 – to provide baseline study for comparison prior to treatment

^d Biopsy within 2 weeks prior to day 1

^e Tetanus immunization to take place any time after leukapheresis and prior to day 1

^f Where chemistry labs indicated, the following serum tests are to be performed: Chem 7 (sodium, potassium, bicarbonate, BUN, creatinine, glucose), ALT, AST, bilirubin, alkaline phosphatase, amylase, TSH (thyroid stimulating hormone), and LDH

^g Procedures can be +/- 7 days of this visit, scans to be done prior to biopsy (and study treatment for Arm 2)

^h Can be +/- 7 days of this visit

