3. Baseline research leukapheresis (50-100 mL approximate total volume, for immunological monitoring) – to take place within 4 weeks prior to day 1.
NOTE: For patients unable to undergo leukapheresis at this time point, a 200-cc blood draw may be substituted (twenty 10-mL green-top heparinized tubes).
4. Tetanus immunization (to take place after baseline leukapheresis and prior to day 1)
5. 20 mL peripheral blood (red-top tubes) for sera to evaluate baseline antibody responses, and 20 mL peripheral blood (green-top tubes) for CTC baseline evaluation
6. FLT PET/CT scan (to occur within 4 weeks prior to day 1).
7. Tissue biopsy – metastatic site – to take place within 2 weeks prior to day 1

C. Immunization #1 (Day 1)

1. Physical examination, symptoms assessment, and ECOG performance score
2. Blood draw for CBC, differential and platelets, chemistry panel, PSA and PAP
3. Subjects will receive pTVG-HP DNA immunizations intradermally on the deltoid area of the lateral arm (preferentially left arm) with 0.25 mL administered at each of two adjacent sites.

4. Following vaccinations, the subjects will be observed for 60 minutes for unanticipated adverse events.
- D. ARM 1 SUBJECTS ONLY: Anti-PD-1 #1 (Day 1, 1-3 hours after day 1 immunization)
1. Pembrolizumab 2 mg/kg administered intravenously over 30 minutes
 2. Subjects will be observed for additional 30 minutes for unanticipated adverse events. Vital signs (temperature, heart rate and blood pressure) will be assessed and recorded by the staff prior to, and at the end of, the treatment period.
- E. Immunization #2 - Day 15 (+/- 3 days)
1. Subjects will receive pTVG-HP DNA immunizations intradermally on the deltoid area of the lateral arm (preferentially left arm) with 0.25 mL administered at each of two adjacent sites.
 2. Following vaccinations, the subjects will be observed for 60 minutes for unanticipated adverse events.
- F. ARM 1 SUBJECTS ONLY: Anti-PD-1 #2 - Day 22 (7 +/- 3 days after day 15 visit)
1. Physical examination, symptoms assessment, and ECOG performance score
 2. Blood draw for CBC, differential and platelets, chemistry panel, PSA and PAP
 3. Pembrolizumab 2 mg/kg administered intravenously over 30 minutes
 4. Subjects will be observed for additional 30 minutes for unanticipated adverse events. Vital signs (temperature, heart rate and blood pressure) will be assessed and recorded by the staff prior to, and at the end of, the treatment period.

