3'-Deoxy-3'-[¹⁸F]Fluorothymidine (FLT) positron emission tomography (PET)/computed tomography (CT) uses a thymidine analogue that accumulates in proliferating tissue. Proliferating tissue could include malignant lesions or immune cells. Following vaccination we have observed a proliferation of CD4+ and CD8+ T cells specific for PAP, at least as assessed *in vitro* following reencounter with the PAP antigen [29, 31]. In a study of patients with melanoma treated intranodally with a dendritic cell vaccine, FLT PET/CT could detect uptake in treated lymph nodes compared to control lymph nodes following vaccination, uptake that persisted for up to 3 weeks [78]. Consequently, FLT PET/CT may be useful as a molecular imaging tool to detect immune activation after immunization, at the same time as detecting decreases in proliferating tumor masses as a result of treatment. We hypothesize that FLT PET/CT will be able to detect increased uptake in left axillary draining lymph nodes (draining site of intradermal immunization) at 12 weeks compared with pre-treatment studies, and that a decrease in uptake will be observed in soft tissue metastatic deposits. FLT PET/CT will be performed at baseline (within 4 weeks of starting treatment) and at week 12, thus enabling comparative evaluation with other imaging obtained at that time and biopsy results.

FLT PET/CT IMAGING PROCEDURES: To ensure uniformity as well as optimal data interpretation, analyses will be conducted under the supervision of [name], PhD (co-investigator) at the University of Wisconsin Image Analysis Core (IMAC) facility, with all radiographic analysis by [name] and designees blinded to study treatment arm.

- At the beginning of each imaging session, a CT scan will be obtained on the combined PET/CT scanner. The CT scan is an integral part of the PET/CT acquisition and serves for attenuation correction calculations and better PET/CT image co-registration. It will enable better delineation of the patient anatomy, which will be important when comparing different scans. An FLT-PET scan will follow. The patients will be injected up to 15 mCi (555 MBq) of ¹⁸F-FLT.

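### The plan allows the baseline FLT PET/CT to follow the tetanus booster, so the pre-treatment node reading may come after another vaccine (minor: node part of exploratory objective 7 only)

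*Combined protocol and SAP*

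**What the plan says.** **Booster.** Section 9.B (Arms 1 and 2) and Section 9.V (Arm 3) use the same words: "Tetanus immunization (to take place after baseline leukapheresis and prior to day 1". Calendar footnote e is looser still: "Tetanus immunization to take place any time after leukapheresis and prior to day 1". Baseline leukapheresis is itself "to take place within 4 weeks prior to day 1". Section 14.A.6 gives the route as intramuscular and names no limb or side.

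**Baseline scan.** Section 9.B: "FLT PET/CT scan (to occur within 4 weeks prior to day 1". Calendar footnote c gives the same window and the purpose: "to provide baseline study for comparison prior to treatment".

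**Hypothesis.** Section 10.E says FLT accumulates in proliferating tissue, which may include immune cells. It expects "increased uptake in left axillary draining lymph nodes (draining site of intradermal immunization) at 12 weeks compared with pre-treatment studies". The study vaccine goes into the deltoid area, preferentially of the left arm.

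**Analysis.** Section 11.F.6.7 tests within-patient change in log SUV by a paired t-test, covering major lymph node groups as well as soft tissue lesions. Section 9 requires up to 6 subjects per arm to complete both scans. Arm 4 has no FLT PET.

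**The concern.** The booster's place after leukapheresis keeps the baseline leukapheresis cells free of its effect. No matching rule protects the baseline scan. The node hypothesis is a rise from baseline to week 12, read as a sign that the study vaccine has activated the draining nodes. If another vaccine has already raised uptake in those nodes at baseline, the measured rise is too small, and a real signal could be read as absent. Section 9 and the calendars ask for no record of the booster's side or of the interval from booster to scan, so an affected pair could not be identified afterwards.

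**Working it through.** **1. What the windows allow.** Leukapheresis may be as early as 28 days before Day 1, the booster may follow at once, and the scan may fall on any day up to Day 1. A scan from 0 to about 27 days after the booster is therefore within protocol, and that range includes the first 21 days.

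**2. Whether the order is fixed elsewhere.** Section 9.B lists leukapheresis (item 3), tetanus (item 4), blood (item 5), FLT PET (item 6). Section 9.V keeps that sequence. The Arm 1 to 3 calendars list leukapheresis, then FLT PET, then biopsy, then tetanus. The two sources list the items in opposite order and neither states a sequence, so neither shows what is done in practice. The protocol does set scan order at month 3 (before biopsy and, in Arm 2, before pembrolizumab), but it has no such rule against the booster.

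**3. What supports a booster effect on the nodes.** Two statements bear on it. Section 10.E cites a melanoma study in which a dendritic cell product was injected into the node itself: "FLT PET/CT could detect uptake in treated lymph nodes compared to control lymph nodes following vaccination, uptake that persisted for up to 3 weeks". Section 14.A.6 includes lymphadenopathy among rare potential side effects of the booster. There are no FLT data after an intramuscular tetanus booster.

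**4. Conditions for bias in one patient.** All four must hold: booster before scan; booster on the side of the study vaccine; a rise in FLT node uptake from the booster; and persistence of that rise to the scan. The documents permit the first, are silent on the second, and support the third and fourth only by analogy.

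**5. Illustrative size.** The plan gives no power figure for FLT PET, so there is none to reproduce.

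- From the plan: n = 6 pairs (Section 9), paired t-test (F.6.7), two-sided 0.05 (F.1).
- Assumed: true standardized rise d = 1.5; k patients meet all four conditions; the booster masks a fraction r of the rise in each.
- Expected mean change = d × (1 − r × k/6). With r = 1 and k = 3: 1.5 × (1 − 3/6) = 0.75, half the true rise. With r = 0.5 and k = 3: 1.5 × (1 − 1.5/6) = 1.125.
- Power by simulation of six differences with unit SD, k of them shifted down by r × d, rejecting when |t| exceeds 2.571 on 5 degrees of freedom:

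| Fraction masked | k = 0 | k = 1 | k = 2 | k = 3 |
|---|---|---|---|---|
| all (r = 1) | 83% | 56% | 32% | 16% |
| half (r = 0.5) | 83% | 74% | 64% | 54% |
| quarter (r = 0.25) | 83% | 79% | 75–76% | 72% |

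With d = 2.0 and full masking, the row is 97%, 75%, 42% and 20%.

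**The case against.** The strongest case against is that the chain from schedule to bias is mostly unproven. The 3-week figure concerns uptake in nodes that were themselves injected with a dendritic cell vaccine, whereas the booster is a single intramuscular dose. Lymphadenopathy is listed as rare. A booster in the right arm would leave the left axilla alone. Full masking supposes that one booster raises uptake as much as six intradermal DNA and GM-CSF vaccinations do in Arms 1 and 2. The objective is exploratory, with no FLT power claim and no multiplicity control, and booster timing is not tied to arm. All of this stands, and it limits the size and severity of the point.

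It does not close the gap. The words in footnote c about a baseline before treatment do not help, because a scan after the booster but before Day 1 also satisfies them. The protocol itself uses the 3-week finding as motivation for looking at nodes after a different, intradermal vaccine, so applying it to the booster is the same kind of inference, though still only an inference.

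A reader might infer from the Section 9 lists that sites give the booster first and usually scan within three weeks of it. The documents do not support that: the calendars list the items the other way round, and no frequency is given anywhere.

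**Conclusion.** The concern holds as a permitted ordering that could bias an exploratory measurement. It does not show that the node analysis is biased. In Arms 1 to 3 nothing stops the baseline FLT scan from following the booster, and nothing records whether it did. Where all four conditions hold, that patient's node change is biased toward zero.

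A reader might take the fall from 83% to 16% as the expected loss. It is the worst case, with three of six patients affected and the whole rise masked. With a quarter masked, the same three patients bring power only to 72%; with a right-arm booster or no lasting uptake there is no loss in the left axilla. Rise, masking and number affected are all assumptions.

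Tumor FLT uptake, safety, progression-free survival and response are untouched. Severity: minor.

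**What to change.** In Sections 9.B and 9.V and in calendar footnotes c and e, state that in patients having FLT PET the baseline scan is done before the tetanus booster. This fits the existing four-week window and adds no procedure.

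For scans already done, record the booster date and side. Keep the F.6.7 nodal analysis as planned and repeat it as a sensitivity analysis without same-side nodes scanned after a booster.

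Costs: slightly tighter scheduling for up to about 6 patients per arm, and fewer pairs, hence less power, in the sensitivity analysis. The ordering rule reaches only FLT patients not yet scanned. Section 6.A closes Arms 1 and 2 once Arm 3 opens, and Section 2.F reports 11 patients accrued to Arm 3 by January 2018. For patients already scanned, the recorded date and side are the useful part.

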^e Tetanus immunization to take place any time after leukapheresis and prior to day 1

^f Where chemistry labs indicated, the following serum tests are to be performed: Chem 7 (sodium, potassium, bicarbonate, BUN, creatinine, glucose), ALT, AST, bilirubin, alkaline phosphatase, amylase, TSH (thyroid stimulating hormone), and LDH

^g Procedures can be +/- 7 days of this visit; scans to be done prior to biopsy (and study treatment for Arm 2)

^h Can be +/- 7 days of this visit

ⁱ Can be +/- 7 days of this visit, and not required if this is off-study visit and previous scans already confirmed disease progression

^j CT of chest at this time point only as clinically indicated

^k PT/INR only required for those subjects who will be undergoing a biopsy. May be performed up to 30 days prior to biopsy, required same day if subject is on coumadin^l If NaF PET/CT is available as standard of care procedure, this may be substituted for bone scan (bone scintigraphy), however all pre-treatment and post-treatment tests must use the same modality (NaF PET/CT or bone scintigraphy)

^m See section 9 for whether or not biopsy and FLT PET is required.

Plan of Treatment: ARM 3 – EXTENDED TREATMENT COHORT

Vaccine / Treatment Visit:	SCREENING		Day 1	Week 3 (21 +/- 3 days from Day 1)	Week 6 (21 +/- 3 days from week 3)	Week 9 (21 +/- 3 days from week 6)	Week 12 (21 +/- 3 days from week 9)	Week 15 (21 +/- 3 days from week 12)	Week 18 (21 +/- 3 days from week 15)	Week 21 (21 +/- 3 days from week 18)	Week 24 (21 +/- 3 days from week 21)	Week 27 (21 +/- 3 days from week 24)	Week 30 (21 +/- 3 days from week 27)	Week 33 (21 +/- 3 days from week 30)	Week 36 (21 +/- 3 days from week 33)	Week 39 (21 +/- 3 days from week 36)	Week 42 (21 +/- 3 days from week 39)	Week 45 (21 +/- 3 days from week 42)	END OF STUDY Week 48 (21 +/- 3 days after week 45)	28-Day Follow Up (28 +/- 7 days after off-treatment visit)
	Within 6 wks of day 1	Within 4 wks of day 1																		
History and Physical Exam																				
History	X																			
Consent	X																			
Physical Exam, ECOG PS		X	X		X		X		X		X		X		X		X		X	X
Tox assessment ^a		X	X	X	X	X	X	X	X	X	X	X	X	X	X	X	X	X	X	X
Lab Tests																				
CBC	X		X	X ⁱ	X ⁱ	X ⁱ	X ⁱ	X ⁱ	X ⁱ	X ⁱ	X ⁱ	X ⁱ	X ⁱ	X ⁱ	X ⁱ	X ⁱ	X ⁱ	X ⁱ	X ⁱ	X
Chemistry panel ^f	X		X	X ⁱ	X ⁱ	X ⁱ	X ⁱ	X ⁱ	X ⁱ	X ⁱ	X ⁱ	X ⁱ	X ⁱ	X ⁱ	X ⁱ	X ⁱ	X ⁱ	X ⁱ	X ⁱ	X
PT/INR		X ^k					X ^k													
Serum testosterone	X																			

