PSA and PAP	X		X	X ⁱ	X ⁱ	X ⁱ	X ⁱ	X ⁱ	X ⁱ	X ⁱ	X ⁱ	X ⁱ	X ⁱ	X ⁱ	X ⁱ	X ⁱ	X ⁱ	X ⁱ	X ⁱ	X
Procedures																				
CT chest/abdomen/pelvis	X						X ^g				X ^h				X ^h					X ^h
Bone scan	X						X ^g				X ^h				X ^h					X ^h
Leukapheresis		X ^b									X ^{bh}									
FLT PET scan ^m		X ^c					X ^g													
NaF PET/CT scan ^m		X			X ^g		X ^g													
Tissue biopsy ^m		X ^d					X ^g													
Tetanus immunization		X ^e																		
Blood for immune analyses		X			X		X				X				X					X (X) ⁿ
Blood for CTC analysis		X			X		X				X				X					X (X) ⁿ
Treatments																				
DNA immunization			X	X	X	X	X	X	X	X	X	X	X	X	X	X	X	X		
Pembrolizumab infusion			X	X	X	X	X	X	X	X	X	X	X	X	X	X	X	X		

^a Study coordinator or research nurse review of systems

^b For patients unable to undergo leukapheresis, a 200-mL blood draw (green top tubes) may be performed instead

^c FLT PET scan – within 4 weeks (28 days) of day 1 – to provide baseline study for comparison prior to treatment

^d Biopsy within 2 weeks prior to day 1

^e Tetanus immunization to take place any time after leukapheresis and prior to day 1

^f Where chemistry labs indicated, the following serum tests are to be performed: Chem 7 (sodium, potassium, bicarbonate, BUN, creatinine, glucose), ALT, AST, bilirubin, alkaline phosphatase, amylase, TSH (thyroid stimulating hormone), and LDH

^g Procedures can be +/- 7 days of this visit; scans to be done prior to biopsy

^h Can be +/- 7 days of this visit

ⁱ Blood draws can be up to 3 days prior to this visit

^j CT of chest at this time point only as clinically indicated

^k PT/INR only required for those subjects who will be undergoing a biopsy. May be performed up to 30 days prior to biopsy, required same day if subject is on coumadin

^m See section 9 for whether or not biopsy, FLT, or NaF PET is required.

ⁿ Blood collected for immune analysis only if not collected within previous 60 days

Plan of Treatment: ARM 4 – EXTENDED TREATMENT COHORT

Vaccine / Treatment Visit	Screening																													

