Logistically, patients will be scheduled for a CT-guided biopsy of a bone or soft tissue abnormality consistent with prostate cancer metastasis. This site of biopsy will be determined by the interventional radiology staff in conjunction with the local PI after review of available scans (bone scans, CT scans, MRI), with preference given to lesions meeting the following factors: (1) size of lesion (preference towards the largest lesion, given the need for biopsy and re-biopsy after 12 weeks); (2) safety of biopsy (with obvious preference to lesions with the least risk to the patient); and (3) for bone lesions with the greatest intensity activity noted on bone scintigraphy. Coordination and acquisition of biopsy material will be performed by the UWCCC TSB (Translational Science Biocore). Standard laboratory tests to assess bleeding and coagulation will also be completed prior to the procedure. Conscious sedation will be used as necessary (typically by using intravenous fentanyl and midazolam) and with appropriate nursing support. In order to obtain adequate tumor sample, and as long as it is deemed safe, and based on accessibility, target lesion size, specimen integrity, specimen appearance, and intraprocedural bleeding, an attempt will be made to obtain 2-6 biopsy samples. Biopsies will be performed using sterile technique and lidocaine local anesthetic. For bone lesions, at least an 11-13 gauge bone-cutting needle, with or without a co-axial trocar, will be used. 2-6 biopsy samples will be obtained of the selected lesion, with multiple samples obtained by: 1) sequential advancement of needle passes through a fixed

trocar, such that each needle pass progresses more deeply into the bone lesion; or 2) re-insertion and re-direction of the needle and/or trocar through another region of the bone lesion. At the completion of the procedure, CT imaging will be repeated to assess for immediate complications. The patient will be observed for 2-4 hours before discharge.

Samples will be transported to the UWCCC TRIP (Translational Research Initiatives in Pathology) lab for formalin fixation, paraffin embedding, sectioning, H&E staining, and ultimately for IHC analysis as described above. Other types of gene expression profiling may be used as well to evaluate gene expression changes, and changes in T cell subtypes infiltrating tumors prior to and after treatment.

E. FLT PET/CT Imaging

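### Scans must precede biopsy at week 12, but no order is set at baseline, so a baseline FLT PET can follow biopsy of a lesion whose FLT change is then analysed

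*Combined protocol and SAP*

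**What the plan says.** **Week 12.** In the Arm 1 calendar, footnote g is attached to both the FLT PET and the biopsy at day 85: "Procedures can be +/- 7 days of this visit, scans to be done prior to biopsy (and study treatment for Arm 2"). Arm 2 carries the same rule. The Arm 3 footnote for week 12 reads "Procedures can be +/- 7 days of this visit; scans to be done prior to biopsy". The rule stands in the calendar footnotes only; Sections 9.M and 9.Z do not repeat it.

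**Baseline.** The FLT PET carries footnote c (within 28 days of Day 1, before treatment) and the biopsy footnote d (within 2 weeks of Day 1). Section 9.B gives the same windows: item 6 is "FLT PET/CT scan (to occur within 4 weeks prior to day 1"), and item 7 has the biopsy "to take place within 2 weeks prior to day 1". Section 9.V does the same for Arm 3. None of these sets an order between the two.

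**Lesion and analysis.** Section 10.D chooses the biopsy site with "preference towards the largest lesion, given the need for biopsy and re-biopsy after 12 weeks" and aims for 2-6 samples from bone or soft tissue. Section 10.E analyses up to five metastases, each segmented individually, and does not exclude the biopsied one. On the tracer it says "Proliferating tissue could include malignant lesions or immune cells", and it hypothesises a fall in uptake in soft-tissue metastases at week 12. Section 11.F.6.7 tests change in log SUV with a paired t-test, within each arm and for both arms combined, and also compares changes between arms.

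**The concern.** A before-after comparison needs both measurements taken under the same conditions. Here the follow-up scan is protected from the repeat biopsy, but the baseline scan is not protected from the first one. In some patients the baseline uptake of a lesion may be read within two weeks after it was cored.

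By the protocol's own account FLT marks proliferating tissue, immune cells included. A local reaction to sampling could raise the baseline value, and its later resolution would look like part of the hypothesised fall. Removing tumor tissue could instead lower the baseline and hide a real fall. Either way, the change in that lesion mixes treatment with the order of procedures, and a paired test within an arm cannot separate them.

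**Working it through.** The plan states no power or precision figure for the FLT endpoint, so there is none to reproduce.

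**Step 1. Is an order implied at baseline?**

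| | Baseline | Day 85 / week 12 |
|---|---|---|
| FLT PET | 28 days before Day 1 (footnote c, 9.B, 9.V) | within 7 days of the visit (footnote g) |
| Biopsy | 14 days before Day 1 (footnote d, 9.B, 9.V) | within 7 days of the visit (footnote g) |
| Order | none | scans first (footnote g) |

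List numbering does not supply one. Where Section 9.B wants an order it says so: the tetanus booster must follow the leukapheresis. Nor does site selection force the scan first, since Section 10.D uses bone scans, CT and MRI, not FLT PET. The windows overlap for the full 14 days before Day 1.

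**Step 2. How often could the scan follow the biopsy?** Assume dates uniform over the windows.

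- Scan within the last 14 of 28 days: 14/28 = 0.50.
- Given that, both dates are uniform on the same 14 days, so the scan is the later one with probability 0.50.
- Product: 0.50 x 0.50 = 0.25 (simulation of one million pairs: 0.250).

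If scans are also booked in the last 14 days, the figure is 0.50. If staff scan first anyway, it is 0.

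**Step 3. How many patients?** Section 9 asks for up to 6 FLT patients per arm.

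- Every FLT patient biopsied: 6 x 0.25 = 1.5 per arm.
- Half biopsied (an assumption): 6 x 0.5 x 0.25 = 0.75 per arm.

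Section 9 sets the biopsy target (at least 6 with paired biopsies per arm) separately from the FLT target and does not require the same patients, so 1.5 is the ceiling for uniform dates.

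**Step 4. What could it do to the test?** This is illustration only, with assumed inputs: no true change; a rise *a* of 10-40% in the biopsied lesion when it is scanned after biopsy; a share *q* = 0.25 of patients affected; log SUV averaged over *L* lesions; SD of log change 0.15-0.25; two-sided 0.05.

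Apparent change = (1 + a)^(-q/L) - 1. For L = 1, 1.10^(-0.25) - 1 = -2.4% and 1.40^(-0.25) - 1 = -8.1%.

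| n | L | Apparent fall | Chance of a false significant fall (nominal 2.5%) |
|---|---|---|---|
| 6 (one arm) | 1 | 2.4-8.1% | 3.9-8.9% |
| 6 | 5 | 0.5-1.7% | 2.7-4.0% |
| 12 (two arms pooled) | 1 | 2.4-8.1% | 4.7-21.3% |
| 12 | 5 | 0.5-1.7% | 2.9-5.3% |

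If every scan followed the biopsy of a sole lesion (q = 1, L = 1, n = 6), the apparent fall would be 9.1-28.6% and the false-positive rate 11.6-99.0%. That is an extreme, not an expectation. If biopsy lowered uptake by the factor 1/(1 + a), the bias on the log scale would have the same size and the opposite sign.

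**The case against.** **The mechanism is not in the documents.** Section 10.E mentions immune cells in connection with vaccine-induced T-cell proliferation. Nothing says that core biopsy raises FLT uptake, by how much or for how long. A reader might infer that the scheduling gap would fake the hypothesised fall. The documents do not support that, because removal of tissue could push the other way. This stands: only the possibility of bias, in an unknown direction, follows.

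**The lesion may be outside the hypothesis.** Biopsies may be of bone, while the FLT hypothesis and Section 11.F.6.7 concern soft-tissue lesions and lymph nodes. This stands too. Even a relevant lesion may be only one of five.

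**The randomised comparison is a control.** Arms 1 and 2 have identical baseline windows, so the gap does not favour either arm systematically. This stands, and it confines the concern to the within-arm and pooled tests.

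**Little hangs on it.** FLT is exploratory objective 7, Section 6.B bars its use for individual treatment decisions on progression, Arms 1 and 2 close once Arm 3 opens, and Arm 4 has neither FLT PET nor biopsy. This limits the priority and the reach of a scheduling change. It does not answer the inconsistency, since the plan imposes the order at week 12 and the dates allow an analysis remedy.

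**Conclusion.** The asymmetry is real: scan before biopsy is required at day 85/week 12 in Arms 1 to 3, and no order is set at baseline, where the windows overlap. As written, the plan lets one end of a paired FLT comparison be measured shortly after a biopsy and the other before the repeat biopsy, in the same lesion.

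The exposure is narrow: exploratory within-arm and pooled comparisons, patients who have both procedures, and biopsied soft-tissue or nodal lesions. About 25% of baseline scans, 1-2 of 6 per arm, is the ceiling if dates are uniform and every FLT patient is biopsied. It should not be read as an estimate of what happened; the recorded dates would show that. The size and direction of any effect on uptake are unknown, and the ranges in Step 4 rest on assumed values. This is a minor point, worth correcting because the correction is nearly free.

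**What to change.** 1. **Patients still to be enrolled in an arm with both procedures:** extend footnote g's order to screening, so that the baseline FLT PET precedes the baseline biopsy, and say so in the matching Section 9 text (9.B, 9.V). This makes the share of baseline scans taken after a biopsy zero. It needs no extra scan, biopsy or visit, only a scheduling constraint within the existing windows.
2. **Scans already done:** compare the recorded FLT and biopsy dates. Where the biopsy came first, exclude the biopsied lesion from the FLT change analysis, or do so as a sensitivity analysis. Section 10.E already treats lesions individually, and the week-12 biopsy returns to the same lesion, so it can be identified. Write this into the detailed SAP that Section 11.F.1 says is still to come, and report how many patients are affected. The cost is one lesion in a few patients; a patient whose only measured lesion was biopsied first would drop out of that analysis.
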